4.2 SCIENTIFIC RATIONALE FOR STUDY DESIGN

Liver cancer is the sixth most common malignancy worldwide. This includes hepatocellular carcinoma (HCC) as the most common type of primary liver neoplasm and CRC as the major source of metastasis to the liver. The incidence of HCC and CRC is increasing rapidly, particularly in Western countries. Imaging plays a pivotal part in the diagnosis of HCC, intrahepatic colorectal cancer (CRC), and other liver malignancies; contrast-enhanced cross sectional imaging can often accurately diagnose the tumor non-invasively. Those lesions that are unable to be characterized non-invasively, however, require biopsy for tissue confirmation of malignancy. By providing a definitive diagnosis, focal image guided biopsy is an indispensable component of the care of patients with cirrhosis. Biopsy can also determine the suitability of minimally invasive therapies for HCC, intrahepatic CRC, and other liver malignancies such as thermal ablation or chemoembolization.

Biopsy is not considered a “perfect” test, and a negative biopsy does not exclude the diagnosis of liver malignancies such as HCC or metastatic CRC (3), due to the potential for sampling error. Small hepatic lesions less than 3cm can pose unique biopsy challenge. MRI visible liver lesions are not always visible by ultrasound or CT, the two available modalities in IR and thus may be

“invisible” to the Interventional Radiologist during the procedure. Patient habitus or underlying liver disease can hinder ultrasound detection of small lesions vis a vie overlying adipose tissue in obese patients and the echogenicity of hepatic parenchyma in cirrhotic patients. In CT-guided procedures, an important limitation is the beam-hardening artifact caused by the biopsy needle. At the critical moment when the biopsy needle is in the vicinity of the lesion, this artifact can obscure the lesion and decrease the Interventionalist’s confidence in the accurate location of the biopsy target. Indeed, in a retrospective study, up to 45% of small hepatic lesions were insufficiently visualized with the biopsy needle in place (4). The negative predictive value (NPV) in one study was only 63%; that is, 37% of patients with benign biopsies were subsequently found to have malignant lesions at the attempted site of biopsy. In a large series from a partner hospital / institution, the NPV for biopsy of small hepatic lesions was 72% (1): over a quarter of the benign biopsies were in fact false negatives. Confidence in the accuracy of a focal hepatic biopsy is essential to diagnosis, staging, and triage of care, as a false negative biopsy can have a devastating impact on a patient’s outcome. Multiple attempts have been made to improve biopsy accuracy. For example, some institutions perform cytological “wet reads” by examining the biopsy tissue under a microscope, while the patient is still on the scanner table. However, this additional step adds a considerable amount of procedural and sedation time and may not always predict the final biopsy result.

We propose a trial to determine the feasibility of using optical molecular imaging (a low cost, real-time, high resolution imaging discipline) for minimally invasive liver biopsy guidance in patients with diagnosed or suspected HCC or metastatic CRC. Patients who require a clinically indicated or separately IRB approved research liver biopsy would after consent, have the OMI performed during biopsy but not as the primary directorate to the biopsy site. The standard of care imaging and cognitive registration would be employed for navigation or guidance of needle and OMI would act as a bystander. Nonetheless, data from OMI imaging would be obtained and evaluated with ex vivo POC OMI and histopathology. Correlations from these studies might support a future larger clinical trial, with different goals that might not exclude efficacy and safety, or even allow for guidance of the needle if separately IRB-approved.

5 STUDY POPULATION

The target study population is patients with focal hepatic lesions with imaging features suspicious for hepatocellular carcinoma or other metastatic liver disease. A radiologist will review patients’ imaging for disease appropriate for biopsy. The decision to refer the patient to enroll in this study may occur between during tumor boards or other clinical care meeting where the primary care team, consults with a CC Interventional Radiologist/ AI or PI, Chief of CC/Interventional Radiology.

5.1 INCLUSION CRITERIA

In order to be eligible to participate in this study, an individual must meet all of the following criteria:

- Patients must have imaging findings consistent with hepatocellular carcinoma or other liver neoplasms or metastasis, for whom image-guided percutaneous biopsy is planned as clinically indicated or IRB-approved under a separate research protocol.
- Patients must have at least one lesion that can readily be biopsied per Principal Investigator.

- Age >18 years.
- Patients must have the ability to understand and the willingness to sign a written informed consent document.
- Evidence of post-menopausal status or negative urinary or serum pregnancy test for female pre-menopausal patients. Women will be considered post-menopausal if they verbally report amenorrhea for 12 months without an alternative medical cause, or have had surgery or received chemicals to induce menopause.

5.2 EXCLUSION CRITERIA

- History of hypersensitivity reactions to Indocyanine Green (ICG), iodinated contrast, or sulfur-containing compounds.
- Pregnant women and nursing mothers are excluded from this study because of exposure to radiation from CT scanning associated with the biopsy
- Uncontrolled intercurrent illness including, but not limited to, ongoing or active infection, symptomatic congestive heart failure, unstable angina pectoris, uncontrolled cardiac arrhythmia, or psychiatric illness/social situations that, in the opinion of the Principal Investigator, would limit compliance with study requirements

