6 STUDY INTERVENTION

6.1 STUDY INTERVENTIONS ADMINISTRATION

ICG is a clinical fluorescent imaging contrast agent and will be ordered from the CC Pharmacy.

Incidence of 1% to 10%: diaphoresis, headache, pruritus, skin discoloration at the intravenous site. In subjects allergic to iodine anaphylactic reactions have occurred. The total dose to be administered will not exceed 40 mg per day. Doses of up to 5 mg/kg have been administered routinely in Japan without adverse reactions. All adverse events experienced by participants will be collected from the time ICG is administered through the end of the procedure. Participants continuing to experience toxicity will be assessed until toxicity has resolved or deemed irreversible.

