6.1.4 Dosing and Administration

6.1.4.1 Pre-Procedure and ICG Administration

ICG was first FDA cleared in 1959. ICG (IC-Green™ Akorn, Inc. Buffalo Grove, IL) (ICG C43H47N2NaO6S2 Molecular Weight 775) is a water-soluble, tricarbocyanine dye routinely used in dilution studies, hepatic and cardiac function studies and ophthalmic retinal fluoroscopy (20). ICG contains not more than 5% sodium iodide. ICG is indicated for determining cardiac output, hepatic function and liver blood flow, and for ophthalmic angiography. In this study, ICG may be used to roughly determine local tissue hepatic function, after the procedure, for data correlation.

ICG has been shown to localize to HCC and intrahepatic tumors 24-72 hours post-injection with high target to background ratios. Doses of ICG up to 5 mg/kg have been administered without adverse reactions. All patients will receive a dose of ICG 0.5mg/kg, with a maximum dose of 40mg, 18-30 hours (roughly 24 hours) prior to the scheduled procedure. Nurses from 3SE Day Hospital will administer ICG as per drug indications.

After receiving ICG, all patients will be monitored for 30 minutes following the injection to identify any acute adverse reaction, after which point they will be free to leave without any dietary or activity restrictions. Patients will receive contact information prior to injection and biopsy. See Section **6.1.4** for ICG administration procedure.

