6.2.2 Formulation, Appearance, Packaging, and Labeling

(https://www.accessdata.fda.gov/drugsatfda_docs/label/2006/011525s017lbl.pdf)

Injection: 25 mg freeze-dried powder in vials supplied with 10 ml aqueous solvent NDC 7478-701-02 (pH 5.5 – 6.5). Manufactured as IC-Green™ Akorn, Inc. Buffalo Grove, IL.

PREPARATION: PHARMACY PREPARATION INSTRUCTIONS (AS PER ICG PACKAGE INSERT): One or two vials of ICG 25 mg will be dissolved with 2 ml diluent, provided by the manufacturer (yielding ICG in solution at 12.5 mg/mL concentration). The CC Pharmacy will prepare the ICG for infusion.

Incidence of 1% to 10%: diaphoresis, headache, pruritus, skin discoloration at the intravenous site. In subjects allergic to iodine anaphylactic reactions have occurred. The total dose to be administered will not exceed 40 mg per day. Doses of up to 5 mg/kg have been administered routinely in Japan without adverse reactions. All adverse events experienced by participants will be collected from the time ICG is administered through the end of the procedure. Participants continuing to experience toxicity will be assessed until toxicity has resolved or deemed irreversible.

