8 STUDY ASSESSMENTS AND PROCEDURES

8.1 SCREENING PROCEDURES

The target study population is patients with focal hepatic lesions with imaging features suspicious for hepatocellular carcinoma or other metastatic liver disease. A radiologist will review patients' imaging for disease appropriate for biopsy. The decision to refer the patient to enroll in this study may occur between during tumor boards or other clinical care meeting where the primary care team, consults with a CC Interventional Radiologist/ AI or PI, Chief of CC/Interventional Radiology.

The research team will review and verify the following available information prior to patient registration on the protocol:

1. Clinical evaluation by referring team/ primary care team
2. Laboratory tests (blood work)
3. Radiology tests with report of focal lesions within the liver and confirmed or suspicious HCC other liver neoplasms or metastasis

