9.3.1 Evaluable for toxicity

The following adverse event management guidelines are intended to ensure the safety of each patient while on the study. The descriptions and grading scales found in the revised NCI Common Terminology Criteria for Adverse Events (CTCAE) version 4.0 will be utilized for AE reporting. All appropriate treatment areas should have access to a copy of the CTCAE version 4.0. A copy of the CTCAE version 4.0 can be downloaded from the CTEP web site (http://ctep.cancer.gov/protocolDevelopment/electronic_applications/ctc.htm#ctc_40).

Incidence of 1% to 10%: diaphoresis, headache, pruritus, skin discoloration at the intravenous site. In subjects allergic to iodine, anaphylaxis reactions have occurred. The total dose administered will not exceed 40 mg per day. Of note, doses of up to 5 mg/kg have been administered as routine in Japan without adverse reactions. All adverse events experienced by participants will be collected from the time ICG is administered, through the study, and until the patient is off treatment.

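### The allergy exclusion in 5.2 omits iodine and iodides, although the protocol names iodine-allergic subjects as the group in which anaphylaxis has occurred

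*Combined protocol and SAP*

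**What the plan says.** Section 5.2 contains one allergy criterion: "History of hypersensitivity reactions to Indocyanine Green (ICG), iodinated contrast, or sulfur-containing compounds". The inclusion criteria in 5.1 say nothing about allergy.

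The protocol describes the risk of the agent in three places. Section 6.1: "In subjects allergic to iodine anaphylactic reactions have occurred". Section 6.2.2: "In subjects allergic to iodine anaphylactic reactions have occurred. The total dose to be administered will not exceed 40 mg per day". Section 9.3.1: "In subjects allergic to iodine, anaphylaxis reactions have occurred".

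Section 6.1.4.1 gives the composition, "ICG contains not more than 5% sodium iodide", and the dosing rule, "All patients will receive a dose of ICG 0.5mg/kg, with a maximum dose of 40mg". It also sets the observation period: "all patients will be monitored for 30 minutes following the injection to identify any acute adverse reaction". After that participants may leave.

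Three other places bear on who is let in:

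- Section 2.4.3 says that those referred and enrolled will have no contraindication to ICG, but lists none.
- Table 1 (1.3) has a general review of medical history at screening.
- Section 8.1 introduces its checks with "The research team will review and verify the following available information prior to patient registration on the protocol" and then lists clinical evaluation by the referring team, laboratory tests and radiology tests.

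**The concern.** The warning and the exclusion do not cover the same people. The warning is about iodine allergy. The exclusion is about three agents, one of which (iodinated contrast) overlaps with iodine allergy but is not the same thing in an eligibility list that staff apply item by item. A participant could therefore belong to the group the protocol itself associates with anaphylaxis and still be eligible.

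This matters more here than where the drug is part of treatment. ICG is given so that optical data can be collected in the background of a biopsy that would take place anyway (2.2, 2.4.3). The fluorescence results are neither shared with participants nor used in their care (9.4.1). With no direct benefit to set against the dose, a risk that the protocol already recognises should be screened out before injection.

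**Working it through.** No sample size, power or error rate is involved, and the plan states no figure to reproduce. The check sets the eligibility text against every mention of iodine, iodide, allergy, hypersensitivity and contraindication in the document.

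**Step 1: who is named as at risk, and who is excluded.**

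| Prior reaction to | Named in the anaphylaxis warning (6.1, 6.2.2, 9.3.1) | Excluded by 5.2 |
|---|---|---|
| ICG | no | yes |
| Iodinated contrast | not by name | yes |
| Sulfur-containing compounds | no | yes |
| Iodine or iodides, with no reaction to the three above | yes | **no** |

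The criterion is wider than the warning in some respects (sulfur compounds, for example) and narrower in one: iodine and iodides. The last row is the gap.

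**Step 2: whether other text closes the gap.**

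- 2.4.3 requires no contraindication to ICG, but it is risk/benefit narrative, defines no contraindication, does not mention iodine, and is not one of the section 5 criteria.
- The history review in Table 1 could bring an iodine reaction to light. Once found, nothing in 5.2 tells the team to exclude the patient.
- The list in 8.1 has no allergy item. This carries little weight on its own, because that list does not name checks for the other exclusions either.
- The 30-minute observation (6.1.4.1) and the off-treatment rule for allergic reactions (7.1) apply only after the dose has been given.

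Some of these may catch a patient in the last row. None of them names iodine or requires exclusion.

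**Step 3: exposure, for context only.** The inputs, all from 6.1.4.1, are 0.5 mg/kg ICG, a 40 mg maximum, and sodium iodide at no more than 5%.

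- Body weight at which the cap is reached: 40 mg ÷ 0.5 mg/kg = 80 kg.
- Upper bound on sodium iodide at the cap: 0.05 × 40 mg = 2.0 mg.
- At an assumed 50 kg: ICG = 0.5 × 50 = 25 mg; sodium iodide at most 0.05 × 25 = 1.25 mg.

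These figures show that an iodide exposure exists and bound it. They do not measure risk, because the documents state no clinically relevant threshold.

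**The case against.** The best defence is that the hazard is already largely covered. Section 5.2 excludes prior reactors to the agent itself and to iodinated contrast, and can be read as the working form of the iodine warning. The protocol never defines iodine allergy or separates it from contrast reactions, and it does not show that the remaining patients exist in any number or react to ICG. A clinician who has read the same warning three times would probably treat a recorded iodine allergy as a contraindication under 2.4.3. In addition, 6.1.4.1 has nurses give ICG according to the drug's indications, 6.2.2 and 6.2.3 link to the product label, and 10.1.1 adds multi-disciplinary review before enrolment. On this view the point is a minor wording edit.

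Part of this stands. The number affected is probably small, the iodide arithmetic says nothing about the probability of a reaction, the silence of 8.1 proves little, and a careful investigator might well decline such a patient.

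The gap nevertheless remains. Relying on 2.4.3 leaves exclusion to individual judgement on an undefined term, and referral depends on the investigator of the primary protocol (5.5), who is given no definition. If the sponsor's view is that contrast reactors are the only relevant group, then it is the warnings in 6.1, 6.2.2 and 9.3.1 that need rewording. Either way the two texts should agree, and with the warnings as they stand the safer repair is to the exclusion.

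**Conclusion.** The concern holds. As written, 5.2 does not exclude a person with a recorded iodine or iodide reaction who has not reacted to ICG, iodinated contrast or sulfur-containing compounds, although the protocol reports anaphylactic reactions in iodine-allergic subjects.

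The size is limited: a probably small, uncounted group, each exposed to at most 2.0 mg sodium iodide, with anaphylaxis as the event of concern. The conclusion rests on the protocol's own warning being taken at face value and on 5.2 being applied literally. Whether an iodine reaction without a contrast reaction predicts a reaction to ICG cannot be settled from these documents.

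This is a participant-safety improvement that should be made. It does not threaten the validity of the trial.

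**What to change.** In the first bullet of 5.2, insert *iodine or iodides* between ICG and iodinated contrast, so that the criterion covers hypersensitivity to all four. Add a matching line to the screening checklist, to be completed at the medical-history review already in Table 1.

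The cost is one phrase, one checklist line and the loss of a very few otherwise eligible patients. The sample size of 77, the endpoints and the analysis stay as they are.

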5.3 INCLUSION OF VULNERABLE PARTICIPANTS

5.3.1 Inclusion of children

HCC is rarely seen in children therefor we will enroll participants > 18 years of age. Children are excluded from this study.

5.3.2 Pregnant Women

Pregnant women and nursing mothers are excluded from this study because of exposure to radiation from CT scanning associated with the biopsy.

5.3.3 Decisionally Impaired

Adults unable to give consent are excluded from enrolling in the protocol. However, re-consent may be necessary and there is a possibility, that subjects could become decisionally impaired. In these cases, the subject will be taken off study.

5.4 LIFESTYLE CONSIDERATIONS

5.4.1 Disease Community Engagement

The research framework of disease community engagement is not applicable to the proposed study. This feasibility study is at its earliest stages. The anticipated results may not be globally useful yet for the target population of the clinical trial.

5.5 SCREEN FAILURES

Recruitment for this protocol is by invitation only; as such referral to this protocol is dependent on the evaluation of the investigator of the primary protocol. Individuals who do not meet the criteria for participation in this study (screen failure) may be considered for rescreen at the discretion of the PI/ referral team. However, patients who have screened, found eligible, signed a consent, and assigned a unique study ID but become ineligible consequently for various reasons

prior to the biopsy, will be considered inevaluable. These patients will be considered a “screen failure” and his/ her unique study ID will be counted towards overall total accrual.

5.6 STRATEGIES FOR RECRUITMENT AND RETENTION

This study will be “Enrolling by Invitation Only”. Patients will be referred by their NIH primary care team and will need to be registered to an existing NIH clinical study prior to enrolling in this study. Any patient who is referred and found eligible for a standard liver biopsy will be able to screen for this study.

5.6.1 Costs

Potential participants will not incur any costs associated with this protocol.

5.6.2 Compensation

Eligible subjects who sign a consent form will be compensated when ICG is administered in accordance with NIH guidelines ([Table 2](#)).

All remuneration will be directed to be paid to the participant. These funds are intended to compensate for time away from work that maybe required to participate in this study and time spent receiving ICG. Payment will be sent after the biopsy procedure. Travel will not be provided or compensated for. We will also not provide remuneration for meals and lodging. If a participant withdraws from study, no future compensation will be made, but prior compensation will not be revoked.

Table 2. Subject Reimbursement Schedule

	Inconvenience units*	Pay for inconvenience	Time (h)	Pay for time	Total pay
Contrast IC/Oral	2	\$20	3	\$40	\$60
Peripheral IV	1	\$10	N/A	\$0	\$10
Screening	3	\$30	N/A	\$0	\$30
TOTAL					\$100
NOTE:	Patient will be paid \$100 when he or she received ICG.				

* Inconvenience unit = \$10

6 STUDY INTERVENTION

6.1 STUDY INTERVENTIONS ADMINISTRATION

ICG is a clinical fluorescent imaging contrast agent and will be ordered from the CC Pharmacy.

Incidence of 1% to 10%: diaphoresis, headache, pruritus, skin discoloration at the intravenous site. In subjects allergic to iodine anaphylactic reactions have occurred. The total dose to be administered will not exceed 40 mg per day. Doses of up to 5 mg/kg have been administered routinely in Japan without adverse reactions. All adverse events experienced by participants will be collected from the time ICG is administered through the end of the procedure. Participants continuing to experience toxicity will be assessed until toxicity has resolved or deemed irreversible.

6.1.1 Study Intervention Description

The study has 2 steps:

- a) In-procedure biopsy
- b) Ex vivo tissue sample analysis outside of procedure (point of care)

6.1.2 In-procedure biopsy

Tumor biopsy is divided into several stages or parts, described below. The first step is the standard of care preparation of the site and imaging of the liver, infiltration of local anesthesia followed by placement of the PercuNav coaxial needle by ultrasound guidance and EM tracking and co-display into the liver parenchyma. The next step requires a very short pause to thread that pediatric scope inside the PercuNav sheath. This is done by removing the PercuNav inner stylet from the hollow sheath. Once the scope is in the sheath, it is advanced in order to allow for signal sampling from normal liver. After acquiring images from normal liver, the scope is removed and once again the PercuNav needle inner stylet is reinserted, and the needle is advanced and manipulated into the target lesion in the usual standard fashion with standard clinical image-guidance. When the target is reached, the same process ensues, with exchange of the inner stylet for the scope, and subsequent repeat ICG OMI imaging occurs again. Finally, the PercuNav stylet is removed and replaced with a standard spring-deployed biopsy needle, and tissue core biopsy sampling occurs. Except for the two pauses, the biopsy procedure occurs as per usual medical practice, with standard clinical image guidance determining the location of biopsy tissue sampling, as is standard practice for many decades at NIH and around the globe. Thus, in summary, in order to record the data (optical study has 2 steps).

